The study is a single-center, prospective assessment of the feasibility, acceptability, and usability of ReCognition VR -based simulated cognitive stimulation to improve attention and focus in surgical patients.

Sample size: We will enroll 30 participants: 15 participants who are ≥60 years of age with traditional orientation methods and 15 participants who are ≥60 years of age and receive ReCognitionVR-based cognitive exercises.

Justification of sample size: The study is a feasibility study expecting that 70% of participants in the study intervention group will complete 20 minutes of the ReCognitionVR-based exercise, where each group will be evaluated separately. Descriptive statistics will be used to summarize the findings; 15 participants in each group will be recruited. The intent is that this study will provide information for a larger, subsequent clinical trial of patients ≥60 years old at risk for delirium.

Data and measures to be taken:

The endpoints for this feasibility study are:

Primary Objective:

Safety/Tolerability: We will examine measures that can inform on the safety of the experience to be used in the subsequent clinical trial. The measures are:

- 1. Mean change from pre to 10 minutes of the ReCognition VR-based exercise in:
 - a. SpO2
 - b. RR
 - c. Blood pressure (Mean BP, Systolic BP, and Diastolic BP)
- 2. Mean change from pre to end of the ReCognition VR-based exercise in:
 - a. SpO2
 - b. RR
 - c. Blood pressure (Mean BP, Systolic BP, and Diastolic BP)

Secondary Objectives:

Feasibility: 70% of participants in each group will complete 20 minutes of use of the ReCognition VR-based software (a binary outcome).

Acceptability: We will measure the acceptability and usability of the experience based on the proportion of participants with a SUS score >35.

VR-games Accuracy: We will report on the proportion of participants who complete the game without any user errors and the number of attempts each participant uses to complete the game.

Page 6 of 21

Exploratory Objective:

Delirium: We will assess delirium using CAM tool⁶ or the 4 A's test⁷. Delirium is defined as any positive CAM Score or/and score of 4 or above on the 4 A's test for 72 hours after study interventions.

Accessing data from medical records:

Medical records of the potential study subjects will be reviewed for medical history for the inclusion and exclusion criteria described below in section 10.

Data analysis plan:

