We will report the demographic variables of age, sex, race, and ethnicity for each group and the clinical characteristics and will review the patient's medical records for body mass index, history of hypertension with active management, drinking status, smoking status, ASA status, preexisting medical co-morbidities. If not found in the medical record, we will obtain this information.

[figure not shown]
The results of this study will be reported using descriptive statistics. Continuous variables will be reported as means with standard deviation or medians and interquartile range contingent on the normality of the distribution. Categorical variables will be reported using Chi-square or Fisher's exact test, as appropriate.

5. Study Intervention

- 1. Older patients (≥ 60 years old) scheduled to undergo abdominal surgeries (open or laparoscopic or robotic assisted), small bowel and large bowel surgery; cholecystectomy; Whipple procedure; pancreatectomy; splenectomy at HMH will be invited to participate.
- 2. We will screen patients for inclusion and exclusion criteria and will assign a screening number.
- 3. After signing informed consent, participants will be enrolled in the study and randomized using computer-generated randomization software to traditional orientation method (control) or ReCognitionVR-based cognitive exercises (experimental).
- 4. The experimental group will watch a video on using VR technology, placement of a VR headset, and assessment of baseline cognitive function using the Mini-Cog screening tool.
- 5. All participants will have a frailty screening assessment.9

Page 7 of 21

- 6. The Mini-Cog screening tool will assess the patient's cognitive status of all participants. (Appendix D)⁸
- 7. The experimental group will receive a 3D- ReCognitionVR-based simulated cognitive exercise program targeting attention, organizing thinking, and motor activities using VR games. The participant will receive study intervention after arrival to the room from the operating room, free of residual anesthesia, by measuring the Richmond Sedation Scale (RASS)- Appendix E^{10} score of 0.

- 8. The detail of the software as follows:
 - 3-D Recognition Virtual Reality-Based Simulation Sessions Program: Software Platform:

The VR platform will consist of

Page 8 of 21

- The VR headsets manufactured by the Oculus Quest 2 glasses (Facebook Inc., USA) with stereoscopic vision and stereo sound will be used to show the virtual world to participants.

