- Motion Sensor
- Flat Screen TV with Software

The VR headsets manufactured by the Oculus Quest 2 glasses (Facebook Inc., USA) with stereoscopic vision and stereo sound will be used to show the VR to study participants. After headset placement, the study participants will be able to follow instructions provided by virtual nurse AVATAR. The participants will receive low cognitive load exercises based on virtual reality techniques, including a relaxed environment, music therapy, time orientation, delivery instructions, and task completion motivation. The exercise task will focus on attention, organized thinking, and motor activities.

9. If you are in the traditional orientation method, you will be visited by a nurse at the start of each nursing shift. The nurse will ask you questions to check your memory and attention. Examples of questions include asking you for your name, the date, where you are, and what just happened to you. This will be repeated during every nurse shift change and is the usual care you would receive, even if you were not in the study. In this method, your vital signs (oxygen levels, how fast you are breathing, and your blood pressure) will be measured at different time points after your abdominal surgery as part of your standard care. When you wake up from surgery, you will have the traditional orientation questions asked of you until you are discharged from the hospital. Your participation in this study will be over after you leave the hospital.

Schedule of Activities

Procedures	Screening*	Day 1,	Day 1,	Day 1,	Day 1,	Post 24	Post 48	Post 72
		Time 1:	Time 2:	Time	Time	hours	hours	hours
		pre	10	3: post	4: end			
			minutes		of			
					study			
Visit number	Visit 0 or 1	Visit 1				Visit 2	Visit 3	Visit 4
Informed	X							
consent								
Demographics	X							
Medical history	X							
Randomization		X						
Administer			X-					
study								
intervention								
Concomitant	X							
medication								
review								

Page 9 of 21

Procedures	Screening*	Day 1, Time 1: pre	Day 1, Time 2: 10 minutes	Day 1, Time 3: post	Day 1, Time 4: end of study	Post 24 hours	Post 48 hours	Post 72 hours
Visit number	Visit 0 or 1	Visit 1				Visit 2	Visit 3	Visit 4
Physical exam (including height and weight)	X							
Frailty screening assessment	X							
Mini-Cog screening assessment	Х							
RASS Score	Х							
Pulse oximetry		X	Х	Х				
Respiratory rate		Х	Χ	Х				
Blood pressure		Х	Χ	Х				
System User Survey					Х			

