Number of software and device re-starts, re-sets.		Х	X					
Number of User errors			Х	Х	Х			
Number of game attempts			X	Х	Х			
Adverse event review and evaluation		Х	Х	Х	Х	Х	X	X
Pain scores (Numeric Pain Scale)	Х	Х	Х	Х	Х	Х	Х	X
Positive CAM or/and 4 A's Test	Х	Х				Х	Х	Х
Complete Case Report Forms (CRFs)	Х	Х			X			

^{*}Screening Visit and Day 1 may occur on the same day

Dosing:

The study participants will receive approximately 20 minutes of VR- based cognitive stimulation sessions and complete a post-user survey System Usability Scale.

Acceptability Survey:

Principal Investigator (PI) or a research team member will use the SUS survey to interview the study participants. (Appendix - F)

6. Drugs, Biologics, Devices

Specifically, VR will be simulated using UNITY software and Oculus Quest (two headsets) for this project. The use of ReCognitionVR software is investigational in this proposal. However, in Phase 1a study we evaluated the feasibility, safety, and acceptability of ReCognitionVR software in healthy elderly subjects. The result of the study is uploaded as a clinical study report in MORTI. Moreover, the use of VR software has been approved by FDA. There are multiple VR softwares that are approved by the FDA. Please see the link below for reference:

Augmented Reality and Virtual Reality in Medical Devices | FDA

7. Collaborative / Multi-site Research

N/A

8. Data Privacy / Confidentiality

Houston Methodist policies for Protected Health Information (PHI) will be followed, including all physical and electronic data security requirements, encrypted devices, and HM password-protected servers.

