All data obtained for the study will be stored in a password-protected spreadsheet on a Methodist server and will only be accessible to IRB-approved investigators and research staff at Houston Methodist. Data will be completely de-identified at the time of collection and sent to the statistician via secure mail for analysis. Research materials will be stored in a password-protected computer system database on a secure server on the Houston Methodist network. Data collected will be transferred and stored on REDCap®, a secure web application for building and managing databases. Study personnel requiring access will have their Login/Password assigned to the project. Access to clinical study information will be based on individuals' roles and responsibilities. All study data will be transmitted over an encrypted SSL (Secure Sockets Layer) connection that requires user authentication. This application is designed to be in full compliance with the International Conference on Harmonization and Good Clinical Practices

Page 11 of 21

(ICH-GCP), the FDA's Code of Federal Regulations (CFR) 21 Part 11 Electronic Record and Electronic Signatures, the FDA's "Guidance: Computerized Systems Used in Clinical Trials," and the Privacy Rule of the Health Insurance Portability and Accountability Act of 1996 (HIPAA).

Houston Methodist Research Institute (HMRI) policy on record retention will be followed, and human subject research data will be kept for a minimum of 6 years after completing the study. Research written materials will be stored in the Department of Surgery Research Office (Skurlock 1150) and electronic materials on password-protected computer systems on a secure server on the Houston Methodist network.

A unique identification code will be assigned to each participant in this study, and the study team will maintain the linking log with the study files. The only individuals who can see un-coded personal health information include the Study Team and the Institutional Review Board at the hospital, employees of the sponsor who check that this study is being done correctly, and regulatory authorities where required by law.

Data to be collected include:

- Sex
- Age
- Race, ethnicity
- Height, weight
- SpO2 (Time Frame: before, during, and after use of ReCognitionVR software; see Schedule of Activities)
- Respiratory rate (Time Frame: before, during, and after use of ReCognitionVR software; see Schedule of Activities)

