Only the minimum amount of personal information needed to conduct this study will be collected regarding participants' privacy interests. Study participants will be informed that the only individuals who can see un-coded personal health information include the following: the Study Doctor, other employees who work on this study (including the Institutional Review Board) at the hospital, employees of the sponsor who check that this study is being done correctly, and

Page 14 of 21

regulatory authorities where required by law. In addition, participants will be carefully informed about the Release of Health Information section in the Informed Consent Form (ICF), which describes who will access their information and how it will be used. We will emphasize that participation in this study is voluntary and that participants can choose at any time to cease participation and revoke authorization to use and disclose their information.

14. Risks to Subjects

The risks below are associated with the use of the Oculus Quest 2 VR Headset Device.

All adverse events (AEs) will be captured and recorded at each time point. We will report AEs as a proportion of study participants who developed AEs.

Specific AEs to be monitored will include:

Neurological AEs: (Cybersickness is defined as new-onset blurry vision, double vision, dizziness, headaches, eye fatigue, drowsiness, disorientation, and apathy) within 5 minutes after starting the study intervention).

Cardiac Adverse Events: New-onset hypotension (SBP <90 mmHg and DBP <60 mmHg), Bradycardia (HR < 50), Tachycardia (HR> 100), and Arrhythmias (Supraventricular or ventricular) with HR> 150 beats per minutes within 5 minutes after the starting of 3D Simulated VR sessions. Or changes >20% from baselines.

Pulmonary Adverse Events: New-onset hypoxia: SpO2 < 88%, Respirator rate > 35 breaths/minute within 5 minutes after starting 3D Simulated VR sessions.

The safety precautions to minimize the risk to participants are as follows:

- *Vital signs BP*, HR, RR, SPO2, and pain scores (using numeric pain rating scale tool) will be monitored before, during, and after using ReCognitionVR software.

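### The vital-sign safety measures are timed only to the VR session, and step 9 and the Schedule of Activities conflict on whether controls get matching readings

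*Combined protocol and SAP*

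**What the plan says.** Section 4 places two sets of vital-sign measures under the primary safety/tolerability objective: "Mean change from pre to 10 minutes of the ReCognition VR-based exercise in" SpO2, respiratory rate (RR) and blood pressure (BP), and "Mean change from pre to end of the ReCognition VR-based exercise in" the same three. The Objectives and Endpoints table in Section 2 lists these changes as secondary. It makes the proportion of treatment-emergent adverse events (TEAE) in each group the primary endpoint. Section 8 gives the collection time as "SpO2 (Time Frame: before, during, and after use of ReCognitionVR software; see Schedule of Activities", with a matching entry for RR.

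The session lasts "approximately 20 minutes of VR- based cognitive stimulation sessions" (Section 5, Dosing). On timing, step 7 of Section 5 says: "The participant will receive study intervention after arrival to the room from the operating room, free of residual anesthesia", judged by a RASS score of 0. No window in hours after surgery is set.

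Patients are "enrolled in the study and randomized using computer-generated randomization software" (step 3), with 15 per arm. Step 9 says that control vital signs "will be measured at different time points after your abdominal surgery as part of your standard care". The Schedule of Activities marks pulse oximetry, RR and BP at Day 1 Time 1 (pre), Time 2 (10 minutes) and Time 3 (post), with no column or footnote by arm.

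Section 14 ties the cardiac and pulmonary events to the first 5 minutes after the VR session starts. The cardiac item adds: "Or changes >20% from baselines".

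**The concern.** SpO2, RR and BP can change after abdominal surgery for reasons unrelated to VR. The randomised control group could show how much they change over the same interval, but only if it is read on the same clock. Every clock in the plan starts from a VR session that controls never have.

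Two results are at stake. The first is the mean change in the VR arm, which Section 4 intends as safety information for the next trial. Without a control series it is a plain before-after change. The second is the primary endpoint. A TEAE proportion is wanted in each group, yet the vital-sign events are defined by a window from VR start or by change from a baseline, and controls have neither a start nor a stated baseline reading.

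**Working it through.** The plan gives no effect size, SD, alpha or power for vital-sign change, so it has no figure to reproduce. The first check is a reading of the text; the second is an illustration.

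**1. The passages side by side**

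| Item | VR arm | Control arm |
|---|---|---|
| Time zero | Session start, in room, RASS 0 | None stated |
| Pre, 10-minute and end readings | Sections 4 and 8, Schedule | Schedule marks them; step 9 describes routine-care readings |
| 5-minute event window | From VR start | Undefined |
| Baseline for the >20% rule | Not named; Time 1 is the natural reading | Not named; no equivalent reading defined |

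The Schedule and step 9 can both hold only if a control time zero exists, and none is written.

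**2. What an uncontrolled change can show at n = 15 per arm**

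Assumptions: no true VR effect, normal data, drift *d* in units of the SD of change. The plan is descriptive, so the 95% interval serves here only as a yardstick.

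- Half-width, VR arm alone: t(0.975, 14)/√15 = 2.145/3.873 = 0.55 SD.
- Half-width, difference between arms: t(0.975, 28) × √(2/15) = 2.048 × 0.365 = 0.75 SD.
- Chance that the VR-arm interval excludes zero: noncentral t, 14 df, noncentrality *d*√15. At *d* = 0.5 this is 0.5 × 3.873 = 1.94.
- Chance that the between-arm interval excludes zero when drift differs by *d* between unmatched windows: noncentral t, 28 df, noncentrality *d*/√(2/15). At *d* = 0.5 this is 0.5/0.365 = 1.37.

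| *d* (SD of change) | VR arm alone | Unmatched arms, drift differing by *d* | Matched arms |
|---|---|---|---|
| 0 | 5% | 5% | 5% |
| 0.2 | 11% | 8% | 5% |
| 0.3 | 19% | 12.5% | 5% |
| 0.5 | 44% | 26% | 5% |
| 0.8 | 82% | 56% | 5% |

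With matched clocks, drift common to both arms cancels in expectation.

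**3. Scale in mmHg, on assumed linear drift of 1 to 4 mmHg per hour**

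- Within a 20-minute session: 1 × 1/3 = 0.3 to 4 × 1/3 = 1.3 mmHg.
- If a 20-minute VR change were set against a control change over 4 hours: bias = rate × (1/3 − 4), which is −3.7 to −14.7 mmHg.
- With 20 minutes in both arms: 0.

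The drift rates and the 4-hour interval are assumptions; the documents give neither.

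**The case against.** The best counter-argument is that the Schedule, the operational table, already marks all three readings for everyone, and that Section 8 points to it. Step 9 is written in the second person, like consent text, and its reference to different time points may mean only various times, not times that differ from the VR arm's. This stands in part. A reader might infer that controls have no pre, 10-minute and post series at all, and the documents do not establish that. They show a conflict and a missing time zero.

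Next, a reader might infer that post-operative drift will be reported as a VR effect. That goes too far. Analysis is descriptive, each group is evaluated separately, and no between-arm vital-sign contrast is planned. Patients must be free of residual anaesthesia, and drift over 20 minutes may be small, as step 3 of the working shows. What stands is that a VR-arm change cannot be separated from drift of unknown size.

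Finally, a reader might infer that controls, on routine ward readings, would have many more chances to cross the >20% limit than VR patients with two scheduled follow-up readings. The documents do not support this. VR patients are inpatients on the same floor and plausibly have routine readings too, and adverse-event review to 72 hours is not split by arm. Under an assumed model (independent SBP readings, mean 130 mmHg, within-patient SD 8 to 12), 18 control readings against 20 VR readings give chances of at least one crossing of 0.21 against 0.22 (SD 8) up to 0.72 against 0.74 (SD 12). The gap is small and puts the VR arm higher.

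**Conclusion.** The point holds as an unresolved conflict with a real consequence. If step 9 governs, the trial randomises 15 controls but cannot use them to interpret the vital-sign changes listed under its primary safety objective, and the vital-sign part of the TEAE proportion has no defined meaning in the control arm. If the Schedule governs, the readings exist on paper but lack a starting point.

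The size cannot be stated from the documents. The 44% figure rests on an assumed drift of half an SD of change, normal data and no VR effect; with little drift it falls towards 5%. The defect in timing does not depend on those assumptions. It should be settled before enrolment, because unmatched readings cannot be recovered afterwards.

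**What to change.** - Reconcile step 9 with the Schedule. State that Times 1 to 3 apply to both arms, and define control time zero at the landmark used for the VR arm (in room, RASS 0). Record the interval from room arrival to Time 1 in both arms, since no window is set.
- Take SpO2, RR and BP in controls at pre, 10 minutes and about 20 minutes.
- Report mean change in each arm and the between-arm difference with a 95% CI.
- For the between-arm comparison of vital-sign-defined events, use the matched readings with Time 1 as baseline. The Schedule prints no reading between pre and 10 minutes, so also state how the 5-minute window is assessed, and count it from time zero in controls.
- Keep recording and reporting all adverse events to 72 hours in both arms. The matched readings should limit only the comparison, not the safety record.

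If matched control readings are not wanted, the plan should say that the VR-arm changes are uncontrolled.

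The cost is three non-invasive readings in 15 controls (45 sets in all), one amendment and a case report form line. The between-arm interval is also wider than the VR-arm interval, at about ±0.75 against ±0.55 SD of change.

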 The secondary objectives are To assess the changes in vital signs during the exercise 	The secondary endpoints are: 1. Mean change from pre to 10 minutes: a. Pulse oximetry oxygen saturation (SpO2) b. Respiratory rate (RR)	Knowing the change in these biometric measures will assist in designing future investigations of patients at risk of
To assess change in vital signs at the end of the exercise	c. Blood pressure (BP) 2. Mean change from pre to end of VR session: a. SpO2 b. RR c. BP	delirium.
To assess the feasibility of VR-based cognitive stimulation exercises in older surgical patients.	using the ReCognitionVR-based cognitive exercise for 20 minutes by 70% of enrolled participants. using the ReCognitionVR-based cognitive exercise for 20 minutes by 70% of enrolled participants.	It is essential to know if participants can complete the exercise since an incomplete experience will prohibit the assessment of the other variables to be measured.
To determine the acceptability of VR-based cognitive stimulation exercises	the proportion of participants with a System Usability Scale (SUS) score >35.	Successful implementation depends on the acceptability of the intervention and is one of the main factors considered before adopting and implementing computerized cognitive software.

Page 3 of 21

OBJECTIVES	ENDPOINTS	JUSTIFICATION FOR ENDPOINTS
 To determine the accuracy of VR-games Technical difficulty with VR software 	 the proportion of participants who complete the game without any user errors. Number of attempts to complete the game. Number of software and device re-starts and re-sets. 	Accuracy is an essential variable in assessing the attention of the study subject. Attention is a prominent cognitive domain involved in delirium. Important to upgrade or incorporate advanced VR software.
Exploratory		
Exploratory outcome to report the episode of delirium	Confusion Assessment Method (CAM) tool (Appendix B) ⁶ or 4 A's Test score (Appendix C) ⁷ will be used to assess delirium.	Knowing the proportion of study subjects with new-onset delirium will assist in designing future investigations of patients at risk of delirium.

3. Background

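### The Schedule marks recording of device and software re-starts only before the session and at 10 minutes, although the endpoint is a count with no time limit and the session lasts about 20 minutes

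*Combined protocol and SAP*

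**What the plan says.** The Objectives and Endpoints table in section 2 lists "Technical difficulty with VR software" among the secondary objectives. Its measure is "Number of software and device re-starts and re-sets", with no time window attached. The stated reason for collecting it is to guide improvement of the software.

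The Dosing paragraph in section 5 gives the session length: "The study participants will receive approximately 20 minutes of VR- based cognitive stimulation sessions".

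The Schedule of Activities in section 5 is the only place that says when re-starts are to be recorded. The row "Number of software and device re-starts, re-sets" is marked at Time 1 (pre) and at the column headed "Day 1, Time 2: 10 minutes". It is blank at "Day 1, Time 3: post", at Time 4 (end of study) and at all later visits. The next two rows, "Number of User errors" and "Number of game attempts", are marked at Time 2, Time 3 and Time 4.

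**The concern.** The endpoint has no time limit, but its last scheduled recording falls at about the middle of the session. Two other measures taken from the same participants in the same session are scheduled through to its end. Staff who follow the Schedule would note re-starts during set-up and the first 10 minutes and would have no scheduled occasion to note any that came later.

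Two things are at stake. First, the reported count could be too low, and the report would not show by how much. Second, it would cover a different window from user errors and game attempts, so the three could not be read together as a description of one session. Both matter to a study meant to inform a larger trial, because the rate of device failure is one of the practical facts such a trial needs.

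**Working it through.** The plan gives no figure for re-starts, so there is nothing to reproduce. The check is a comparison of Schedule rows followed by simple arithmetic.

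**Step 1. Is the row intact?** The Schedule header has nine columns: procedure, screening, Times 1 to 4, and the 24, 48 and 72 hour visits. The re-starts row has nine cells: a label, one blank, two marks and five blanks. The rows for user errors and game attempts also have nine cells. The blanks after Time 2 therefore do not look like a shifted or broken row.

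**Step 2. Day 1 marks side by side.**

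| Row | Time 1 (pre) | Time 2 (10 min) | Time 3 (post) | Time 4 (end) |
|---|---|---|---|---|
| Re-starts and re-sets | X | X | – | – |
| User errors | – | X | X | X |
| Game attempts | – | X | X | X |
| Pulse oximetry, respiratory rate, blood pressure | X | X | X | – |
| Administer study intervention | – | X | – | – |

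**Step 3. Is Time 2 a true mid-session point?** Vital signs are marked separately at 10 minutes and at post. Section 4 defines two distinct changes for them, from pre to 10 minutes and from pre to the end of the exercise. For those rows, Time 2 falls within the session and Time 3 follows it.

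**Step 4. Does other text schedule a later record?**
- The endpoint list in section 4 does not include technical difficulty.
- The list of data to be collected in section 8 does not name re-starts.
- Section 17 says in general terms that data are collected during play, after a minigame. It names neither re-starts nor a post-session record of them.

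**Step 5. Session time without a scheduled record.** 20 − 10 = about 10 minutes, and 10/20 = 50% of session time.

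**Step 6. Share of re-starts lost.** The documents give no rate or timing, so this needs an assumption. Let *r* be a constant rate per minute. The expected in-session count is 20*r*, of which 10*r* falls after minute 10. The share lost is 10*r*/20*r* = 50% of in-session re-starts. If all re-starts came in the first 10 minutes, the loss would be 0%. If all came later, it would be 100%. Re-starts at set-up (Time 1) are recorded in any case, so as a share of the total including set-up the loss can only be the same or smaller.

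**Step 7. Link to feasibility.** Feasibility is a binary outcome: completion of 20 minutes, with a 70% target. With 15 participants in the VR group, 70% is 10.5 people, so 11/15 (73%) meets it and 10/15 (67%) does not. A session that a device failure ends at, say, minute 15 counts as a non-completion whatever the re-starts row records. What may be missing is the cause.

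**The case against.** The strongest reply is that Time 2 may stand for the session as a whole. The row for administering the intervention is marked only there, yet the intervention runs for about 20 minutes. On that reading, re-starts are recorded at set-up and during the session, and nothing is lost. In addition, user errors and game attempts are marked at Time 4, when play should be over, so marks may be occasions for writing something down rather than limits of observation. Section 14 places observers with the participant, and section 17 speaks of collecting data during play. Staff could well keep a running count.

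Part of this stands. The Schedule is ambiguous, and a blank at Time 3 does not prove that nobody would note a late re-start. A reader might infer that everything after minute 10 is certain to be missed. The documents do not support that, because it holds only if Time 2 acts as a cutoff.

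The reply does not remove the point. If Time 2 meant the whole session, the separate post marks for vital signs, user errors and game attempts would be hard to explain. If marks are occasions for recording, re-starts still lack one after the session, while the neighbouring rows have it. No text asks for a running count.

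**Conclusion.** The point holds in a limited form. As written, the Schedule leaves about 10 of the 20 session minutes without a scheduled record of re-starts, while the endpoint has no time limit. If it is followed literally, any error in the count is downward. The count is then not comparable in coverage with user errors and game attempts.

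Three stronger conclusions are tempting, and the documents do not support them:

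- **That half of the re-starts are lost.** The 50% is a share of session time. It becomes a share of in-session re-starts only under an assumed constant rate, and the possible range is 0% to 100%.
- **That late failures would be invisible when feasibility is judged.** A session cut short is still a non-completion in the binary feasibility outcome. Only its technical cause might go unrecorded in this endpoint.
- **That the investigators chose to stop counting at 10 minutes.** Nothing says so. A mismatch between the endpoint table and the Schedule is the simpler explanation.

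The matter is minor. It affects one descriptive count in about 15 VR participants, with no threshold, test or role in the sample size. It is still worth correcting, because a re-start not noted at the time may not be recoverable later.

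**What to change.** In the Schedule of Activities, add a mark at Time 3 (post) to the re-starts and re-sets row. Beside the endpoint in section 2, state that the reported count is cumulative from set-up to the end of the session. A Time 4 mark is not needed once the post-session count is cumulative.

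The cost is one extra entry on the case report form. There is no added procedure, visit or burden on participants.
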